4.6.3.1 Primary Endpoints

PFS-6 using the RANO criteria (see Section 18.2) will be used as primary endpoints.

4.6.3.2.Secondary Endpoints

- Safety of the combination of SGT-53 and Temozolomide.
- PFS, OS
- Anti-tumor activity of the combination of SGT-53 and Temozolomide based upon the RANO criteria.
- The induction of apoptosis by SGT-53 in the tumor (optional procedure).
- Nanoparticle delivery (optional procedure)

4.6.4. Statistical hypothesis and sample size:

A total of 26 patients will be enrolled. A maximum of 6 patients will be enrolled to participate in the optional surgical resection for tumor analysis.

Patients who have received at least one dose of study drug will be considered evaluable for safety and toxicity endpoints. Patients who require a dose interruption or reduction during the initial cycle will remain evaluable for toxicities if the reduction or interruption is due to a DLT. Patients who do not complete one cycle of treatment but do not have a DLT may be replaced as described in more detail in Section 9.6.

The primary endpoint for the trial is PFS6. Progression-free survival will be defined as the time from study enrollment until the time of first occurrence of disease progression, relapse, or death due to disease.

The analysis of the biological correlate data in patients with surgical resection for tumor analysis has the overall goal of providing an increased understanding of the ability of SGT-53 to cross the Blood-brain Barrier and be delivered into tumor cells in the brain. As such, the objective of the tumor analysis is qualitative rather than quantitative. It should be noted that in the Phase I dose escalation trial of SGT-53, the presence of the exogenous wtp53 delivered by SGT-53 was found to be present in the tumors in a DNA dose dependent manner. Moreover, even the lowest dose of SGT-53 (0.6mg DNA/infusion) was not only found to be present in the tumors of the patients, but to have some anti-tumor effect. A DNA dose 6-fold higher (3.6mg DNA/infusion) is being used in this trial.

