Reverse transcription PCR to determine transgene expression is not applicable for these studies because it would not be able to unequivocally establish that the p53 protein detected was from the exogenous transgene. In contrast, since we have designed primers that included part of the plasmid vector backbone, only the exogenous DNA is amplified. This DNA PCR approach was used to detect the presence of the transgene in the tumors in the Phase I trial (See Figures 16 and 17 in Section 4.4.1.1) and will be used for these studies. The presence of at least 30 copies of exogenous p53 in the tumors sample will be considered positive evidence of drug penetration.

All of the patients in the trial will receive the same dosing of the combination of SGT-53 and TMZ (6 doses of SGT-53 and 5 doses of TMZ every 4 weeks for three 4 week cycles) and thus patients with or without surgical resection for tumor analysis will be used for the Simon two stage calculation. Even for the patients who undergo the optional surgical resection for tumor analysis PFS6 is the primary endpoint. No TMZ will be administered during the time these patients receive the two doses of SGT-53 prior to the resection. Exogenous p53 expression is transient. The patients who receive surgery will not begin treatment for 2-3 weeks post-surgery. Previous studies have demonstrated that there is no indication of the exogenous wtp53, even by DNA PCR, after this length of time. Thus, there will be no additional residual DNA present from the two pre-surgery doses of SGT-53 by the time the combination therapy being evaluated is initiated.

According to the Simon Minimax design, our study, with its sample size of n = 26, has a 10% probability of rejecting (a) the hypothesis of a PFS6 15% (P0) (the historical PFS6 rate) and a 70% probability of accepting (1-b) the hypothesis of a PFS-6 of 30% (P1). If two, or fewer of the first 18 patients were progression free at 6 months, PFS-6 would be considered <15% and the study terminated. Otherwise, the study would be completed, the accrual target being 26 patients. If six or fewer of the 26 patients were progression-free at 6 months, then no further investigation of the treatment regimen would be considered warranted. PFS6 and secondary endpoints progression free survival and overall survival will be evaluated using the Kaplan-Meier product-limit survival curve methodology.

4.6.5. Study Objectives:

Primary:

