For grade 2 events of increased bilirubin, AST, ALT, dyspnea, or DIC, the dose of SGT-53 can be held for up to two weeks. If the grade 2 event resolves within two weeks, then infusion of SGT-53 can resume at the same dose per calendar at incident week + 1-2 weeks (i.e., treatment would be made up and moved 1-2 weeks later).

For non-hematological events other than increased bilirubin, AST, ALT, dyspnea, or DIC, participants who develop a > or = to grade 2 toxicity (except for alopecia, or fever, chills, hypotension that respond to treatment) or grade 3 fatigue will discontinue twice-

weekly infusions until the toxicity level reduces to at least grade 1. Infusions will be held for one week intervals, and infusions that are withheld will be made-up (i.e. moved 1-2 weeks later). If the toxicity does not resolve within two weeks, study drug will be discontinued.

In the event that a patient is removed from the study for reasons other than toxicity, they can be replaced at the same dose level.

Patients who go off-treatment after receiving any infusions of SGT-53 will be considered eligible for evaluation of toxicity. Patients withdrawing consent prior to initiation of therapy will be replaced at the same dose level.

9.4.1. Patient follow up after study discontinuation:

All patients who received treatment with SGT-53 must be followed-up for 30 days after discontinuation of study drug. The 30-day follow-up visit should include a physical examination, vital signs, concomitant medications and assessment of AEs/SAEs and Urine analysis. Blood samples will be taken for: Hematology (CBC with differential, platelet count), Chemistries (BUN, Cr, Na⁺, K⁺, CO₂, Cl, Mg⁺⁺, Ca⁺⁺, phosphorus, albumin, alkaline phosphatase, ALT, AST, total bilirubin, total protein, glucose, LDH), PT/PTT, and D-dimer. Patients who permanently discontinue study drug(s) for reasons other than complete response, progression, or death should also have visits approximately every 2 months for the first year that should include a MRI, physical examination, vital signs, and recording of concomitant medications for glioblastoma.

Patients who are withdrawn from study treatment due to a complete response will have the 30-day follow-up visit as described above. Further follow-up visits every 2 months will include only a physical/neurological exam, concomitant medications, vital signs and a MRI.

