Patients will be monitored for response and disease progression with MRI brain scans every 2 cycles (8 weeks) and/or at the end of cycle 3, or earlier if progressive disease is suspected.

All patients who participate in this study will continue treatment with SGT-53 and TMZ after surgery. The following conditions should be satisfied before initiation of treatment with SGT:

- 1) They have recovered from the effects of surgery including adequate wound healing.
- 2) A brain MRI should be done no later than 72 hours in the immediate post-operative period to best assess the extent of residual measurable disease post-operatively.
- 3) The patient has followed the study requirements for birth control and pregnancy testing since the initial pre-operative doses of SGT and TMZ.
- 4) Post-operatively, patients must have adequate bone marrow function (absolute neutrophil count > 1,500/ μ L and platelet count of >100,000/ μ L), normal coagulation profile (PT/PTT), adequate liver function (SGPT, SGOT, and alkaline phosphatase <2.5 times upper limit of normal and bilirubin < 1.5 X upper limit of normal), adequate renal function (BUN or creatinine <1.5 times upper limit of institutional normal within 7 days prior to starting therapy.
- 5) The patient continues to meet all the eligibility criteria of the study outlined above.

10.2.2. Patients Not undergoing Surgical Resection:

Patients who have had surgery for recurrent glioblastoma will follow the guidelines listed above for patients with optional surgical resection for tumor analysis.

If no surgery has been performed, patients will start SGT-53 and TMZ on the morning of Cycle 1 Day 1 (C1D1). Each cycle will consist of 28 days. Patients will return to the clinic for twice weekly (every 3rd or 4th day) infusions of SGT-53 for three weeks (see treatment schedule diagram in section 9.1.1). Temozolomide will be taken daily by mouth daily on days 9-13 of each cycle. During week 4 of each cycle the patient will not

receive any treatments. Patients will return to the clinic on Day 29 (C2D1) and Day 57 (C3D1) for evaluation. If the drug has been well tolerated continued dosing will be permitted even if they appear to be progressing.

Patients will be monitored for response and disease progression with MRI brain scans every 2 cycles (8 weeks) and/or at the end of cycle 3 or earlier if progressive disease is suspected.

10.2.3. All Patients:

Evaluations done at each clinic visit are detailed in Section 18.1.

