Patients will return to clinic at least weekly for assessments (until the last week of protocol therapy). Refer to the Study Calendar, Appendix 18, for evaluations to be completed during each clinic visit. Each clinic visit will include: assessment of vital signs (blood pressure, pulse and temperature). The following will be performed only on a weekly basis (usually on the first visit of each week) unless clinically significant values were obtained at the previous visit: physical exam; assessment of the ECOG/ Karnofsky Performance Status; assessment of concomitant medications; assessment of adverse events; completion of a serum chemistry panel; completion of a CBC with differential. At the beginning of every cycle a urinalysis panel will be completed. A 12-lead ECG and echocardiogram will be performed at baseline. Additional ECGs/ echocardiograms should be obtained on any patient who demonstrates signs or symptoms of myocardial degeneration. Additionally a 12-lead ECG will be performed 2 hours and 24 hours after the first infusion of SGT-53. A 12-lead ECG will be performed weekly (2 hours postinfusion) during the first 2 weeks of cycle 1, and at the End Of Treatment (EOT) visit. If these patients receive additional rounds of SGT-53/Temozolomide a 12-lead ECG will only be performed as necessary and at the EOT visit.

The first two subjects enrolled in this trial under the current protocol will be monitored for PT/PTT, D-dimer and LDH at baseline/screening; in cycle 1 ~20 hours after the first infusion (during the 23 observation period), and weekly during cycle 1, and once in two weeks during cycles 2 and 3 and at the exit visit. If these patients receive additional rounds of SGT-53/Temozolomide PT/PTT, D-dimer and LDH will be monitored once in two weeks during cycle 1 and monthly in cycle 2 and beyond.

Subsequent subjects will be monitored for PT/PTT, D-dimer and LDH at:

- (i) baseline/screening;
- (ii) in cycle 1 (a) ~20 hours after the first infusion (during the 23 observation period)
- (iii) at the exit visit.

Patients who are responding to treatment (at least stable disease by RANO) may receive three additional cycle of SGT-53/temozolomide therapy at investigator's discretion. Alternatively, they may continue on Temozolomide alone at investigator's discretion.

10.2.4. End of Treatment Evaluations (Day 85, at the end of Cycle 6 if the patient received cycles 4-6, or for premature withdrawal/study drug discontinuation)

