Once a patient has completed study treatment, including premature withdrawal/study drug discontinuation, the patient should complete an End of Treatment Visit. During this visit the following assessments will be completed:

- Radiographic tumor measurement
- Complete medical history
- Physical examination (all body systems)
- Karnofsky Performance Status
- Vital signs (temperature, blood pressure, pulse rate, and respiratory rate)
- Concomitant medication assessment
- Serum chemistry including: sodium, chloride, carbon dioxide, potassium, calcium, phosphorous, magnesium, BUN, creatinine, blood sugar (random), albumin, alkaline phosphatase, alanine aminotransferase, aspartate aminotransferase, bilirubin (total, direct), and total protein.
- CBC with differential and platelet counts
- 12-lead electrocardiogram
- Limited Echocardiogram, only if needed
- Urinalysis
- Assessment of adverse events

10.3. **Follow-up**

If the patient was removed from the Study for toxicity, the patient should be followed with weekly clinic visit and laboratory studies as appropriate, at clinical trial site or the patient's local MD, until the AE has resolved to baseline or is documented as irreversible.

All patients who received treatment with SGT-53 must be followed-up for 30 days after discontinuation of study drug. The 30-day follow-up visit should include a physical examination, vital signs, concomitant medications and assessment of AEs/SAEs and Urine analysis. Blood samples will be taken for: Hematology (CBC with differential, platelet count), Chemistries (BUN, Cr, Na⁺, K⁺, CO₂, Cl, Mg⁺⁺, Ca⁺⁺, phosphorus, albumin, alkaline phosphatase, ALT, AST, total bilirubin, total protein, glucose), PT/PTT, D-dimer, LDH.

Patients who permanently discontinue study drug(s) for reasons other than complete response, progression, or death should also have visits approximately every 2 months for the first year that should include a MRI, physical examination, vital signs, and recording of concomitant medications for glioblastoma.

Patients who are withdrawn from study treatment due to a complete response will have the 30-day follow-up visit as described above and in Sections 5 and 9.4.1. Further follow-up visits every 2 months will include only a physical/neurological exam, concomitant medications, vital signs and an MRI.

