10.4. Efficacy Assessments

10.4.1. Progression-Free Survival

The percentage of patients who are alive and progression-free clinically and radiologically 6 and 12 months after starting treatment will be evaluated using the Kaplan-Meier method. Progression is defined by any of the following using the RANO criteria:

- a) >25% increase in sum of the products of perpendicular diameters of enhancing lesions compared with the smallest tumor measurement obtained either at baseline (if no decrease) or best response, on stable or increasing doses of corticosteroids*.
- b) Significant increase in T2/FLAIR non-enhancing lesion on stable or increasing doses of corticosteroids compared with baseline scan or best response after initiation of therapy *not caused by co-morbid events (e.g. radiation therapy, demyelination, ischemic injury, infection, seizures, postoperative changes, or other treatment effects)
- c) Any new lesion

- d) Clear clinical deterioration not attributable to other causes apart from the tumor (e.g. seizures, medication adverse effects, complications of therapy, cerebrovascular events, infection, and so on) or changes in corticosteroid dose
- e) Failure to return for evaluation as a result of death or deteriorating condition
- f) Clear progression of non-measurable disease

Note: All measurable and non-measurable lesions must be assessed using the same techniques as at baseline.

*Stable doses of corticosteroids include patients not on corticosteroids.

10.4.2. Tumor response rate:

The percentage of patients with a complete or partial response 6 and 12 months after starting treatment will be evaluated using the RANO criteria:

Complete response (CR). Requires all of the following

- a) complete disappearance of all enhancing measurable and non-measurable disease sustained for at least 4 weeks
- b) no new lesions
- c) stable or improved non-enhancing (T2/FLAIR) lesions
- d) patients must be off corticosteroids (or on physiologic replacement doses only)
- e) stable or improved clinically

Note: Patients with non-measurable disease only cannot have a complete response; the best response possible is stable disease.

Partial response (PR). Requires all of the following:

- a) >50% decrease compared with baseline in the sum of products of perpendicular diameters of all measurable enhancing lesions sustained for at least 4 weeks
- b) No progression of non-measurable disease
- c) No new lesions

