⁶ Chemistries include: BUN, Cr, Na⁺, K⁺, CO₂, Cl, Mg⁺⁺, Ca⁺⁺, phosphorus, albumin, alkaline phosphatase, ALT, AST, total and direct bilirubin, total protein, glucose and LDH..

⁷ Tumor size will be assessed by MRI at baseline, every 2 cycles (8 weeks) and/or at the end of cycle 3 to determine if the patient is to continue on study.

⁸ Prior to each infusion of SGT-53, subjects will receive the following premedication: dexamethasone (i.v.), a combination of histamine H1 and H2 blockers (i.v.), indocin (p.o.) and acetominophen (p.o.).

⁹ Hematology and Full panel chemistries will be completed at each visit only if they were clinically significant at the previous visit.

TYPE OF EVALUATION													(Cycle 2									
	D1	D2	D3	D4	D5	D6	D7	D8	D9	D10	D11	D12	D13	D14	D15	D16	D17	D18	D19	D20	D21	D22	D23-D28
Informed Consent																							
Physical Examination ¹	Χ							х							х							Х	
Symptom- oriented Exam ¹				Х							Х							Х					
ECG ²																							
limited ECHO																							
Vital Signs	Χ			Х				Х			Х				Х			Х				Х	
Performance Status	Х			Х				Х			Х				Х			х				Х	
Medical History ³	Х			Х				Х			Х				Х			х				Х	
Hematology ⁴ ′ ⁹	Χ							Х							Х							Х	
PT/PTT, D- dimer, ⁵	Х														Х								
Chemistries ^{6,9}	Χ							Х							Х							Х	
Urine Analysis	Χ																						
Serum Pregnancy Test																							
MRI Scan ⁷																							Х
SGT-53 Administration ⁸	Х			Х				Х			х				Х			Х					
Temozolomide Administration									Х	Х	Х	Х	Χ										

¹ Physical examination will be done on 1st visit of each week.

Confidential

Page 99 of 108

² ECG will be performed at baseline; 2 hours and 24 hours after the 1st SGT-53 infusion; weekly (2 hours post-infusion) during the first 2 weeks of Cycle 1 and at the EOT visit when the patient goes off study. If these patients receive additional rounds of SGT-53/Temozolomide a 12-lead ECG will only be performed as necessary and the EOT visit when the patient goes off study.

³ Medical History includes review of concomitant medications and adverse events.

⁴ Hematology values include complete white count (CBC) with differential and platelet count.

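### No MRI or scan window is tied to month 6, and no rule says how scans on either side of it are classed, so PFS6 can be biased in either direction

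*Combined protocol and SAP*

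**What the plan says.** Section 10.4.1 evaluates, by Kaplan-Meier, the percentage of patients "alive and progression-free clinically and radiologically 6 and 12 months after starting treatment". Section 4.6.4 uses the same status for the Simon rule. The trial stops if two or fewer of the first 18 patients are progression-free at 6 months, and the regimen is dropped "If six or fewer of the 26 patients were progression-free at 6 months". The time origin differs between these sections. Section 10.4.1 counts from the start of treatment, while Section 4.6.4 says "Progression-free survival will be defined as the time from study enrollment until the time of first occurrence of disease progression".

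The imaging text is as follows.

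- Section 18.1, footnote on MRI: "Tumor size will be assessed by MRI at baseline, every 2 cycles (8 weeks) and/or at the end of cycle 3". The tables cover cycles 1 to 3 and mark MRI at screening and on days 23-28 of cycles 2 and 3.
- Section 10.2.1 (10.2.2 is equivalent): "MRI brain scans every 2 cycles (8 weeks) and/or at the end of cycle 3, or earlier if progressive disease is suspected".
- Section 10.2.4: "End of Treatment Evaluations (Day 85, at the end of Cycle 6 if the patient received cycles 4-6", with "Radiographic tumor measurement" among the assessments.
- Sections 5, 9.4.1 and 10.3, on patients who have stopped study drug without having progressed, died or reached a complete response: they "should also have visits approximately every 2 months for the first year that should include a MRI". No starting point is given. Complete responders also have MRI every 2 months, again with no starting point. The 30-day visit lists no MRI.

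No section names a month-6 MRI, gives a window around it, or converts 6 months to days.

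**The concern.** A 6-month landmark that depends on imaging needs an image at the landmark, or a rule for patients whose scans fall on either side of it. The plan has neither. A patient scanned clear at day 168 and found to have progressed at day 224 is a PFS6 success if progression is dated to the detecting scan. The same patient is a failure if status at month 6 is read from the first scan after it. Two sites can also place the two-monthly MRI differently and both comply.

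The design is sensitive to this. With 26 patients and a go decision at seven or more, one or two reclassified patients can change the conclusion.

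**Working it through.** **Inputs.** Simon rule: go if more than 2 of 18 and then more than 6 of 26 are progression-free; P0 15%, P1 30%, stated alpha 10% and power 70% (Section 4.6.4). Cycles are 28 days (Section 5). My assumptions: one month is 30.44 days, so month 6 is day 182.6 (about 183) and two months is 61 days; PFS is exponential.

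**The plan's own figures.** P(go | p) is the sum over x = 3 to 18 of P(X1 = x) × P(X2 ≥ 7 − x), with X1 ~ Bin(18, p) and X2 ~ Bin(8, p). This gives 0.083 at 15% and 0.701 at 30%. The design reproduces.

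**Scan days.**

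- Six cycles: 3 × 56 = 168, with End of Treatment imaging at about day 168-169. The next scan is at 168 + 56 = 224 (8-weekly) or 168 + 61 = 229 (two-monthly).
- Three cycles, last scan before month 6 by possible anchor:
  - last infusion (57 + 17 = day 74): 74 + 61 = 135
  - Day 85: 85 + 61 = 146
  - 30 days after the last infusion: 74 + 30 + 61 = 165
  - 30 days after Day 85: 85 + 30 + 61 = 176
  - Day 1: 3 × 61 = 183, no gap
- 8-weekly from the end of cycle 3 (for example on temozolomide alone): 84 + 56 = 140, next 196.
- Resection patients: if time ran from the first pre-surgical infusion, Day 1 would come 3 + 14 = 17 to 3 + 21 = 24 days later. The cycle-6 scan could then fall after month 6.

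**Case A: progression dated to the detecting scan.** Apparent PFS6 is S(d) = p^(d/182.6), where d is the last scan before month 6. If half of the gap progressions are caught clinically, it is p + (S(d) − p)/2. With true p = 0.15 and every patient on the same path:

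| Last scan | S(d) | P(go), none caught | P(go), half caught |
|---|---|---|---|
| day 168 | 0.175 | 0.153 | 0.115 |
| day 169 | 0.173 | 0.147 | 0.112 |
| day 176 | 0.161 | 0.110 | 0.096 |
| day 165 | 0.180 | 0.173 | 0.123 |
| day 146 | 0.219 | 0.337 | 0.190 |
| day 140 | 0.234 | 0.403 | 0.217 |
| day 135 | 0.246 | 0.463 | 0.242 |

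Mixed paths, with splits that are mine because the documents give none: half at day 169 and half scanned at month 6 gives 0.097 (half caught) to 0.112 (none caught); 80% at day 169 and 20% at day 146 gives 0.126 to 0.180. If the hazard is not constant (Weibull shape 0.7 to 1.5), the day-168 figure with none caught runs from 0.129 to 0.200.

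**Case B: status read from the first scan after month 6.** At day 224, a true 15% reads 0.15^(224/182.6) = 0.098, with P(go) 0.010. A true 30% reads 0.30^(224/182.6) = 0.228, with power 0.38 instead of 0.70.

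**The case against.** A reader might infer that PFS6 will be inflated. The documents do not establish that. Upward bias needs progression to be dated to the detecting scan. Section 10.4.3 does this for time to progression, but it is not a PFS6 rule. Section 10.4.2 moves back the last stable scan in one corticosteroid situation only. Section 10.4.1 requires patients to be progression-free radiologically at 6 months, so a strict reader could use the next scan, which gives Case B. This objection stands.

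Day 183 is also an assumption. If 6 months means 24 weeks, the six-cycle scan at day 168 sits on the landmark and that path has no gap. This stands too, although a three-cycle patient anchored at Day 85 would still be last scanned 168 − 146 = 22 days earlier.

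The plan has safeguards against missed progressions: at least weekly visits on therapy (Section 10.2.3), MRI on suspicion, and clinical deterioration or failure to return because of death or decline counted as progression (Section 10.4.1). These shrink Case A. On the six-cycle path the worst case is only 26 × (0.1746 − 0.15) = 0.64 misclassed patients at a true 15%.

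Nor does imaging cease after cycle 3. The tables end there, but the 8-weekly text, End of Treatment imaging and two-monthly follow-up continue. What is missing is a tie to month 6.

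**Conclusion.** The plan should be changed. The primary endpoint has no scheduled radiological assessment at its own time point, no definition of that time point in days, two time origins, and no classing rule for scans that straddle it. These facts do not depend on any model.

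The size does. With month 6 at day 183, exponential PFS and all patients last scanned at day 168-169, detection-date classing gives false-go of about 0.11 (half caught clinically) to 0.15 (none caught), against 0.083 attained and 10% stated. Classing from day 224 gives 0.01, and power of 0.38.

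The 0.34 to 0.46 values at days 146 to 135 are tempting to quote. They require every patient to be on that single path with no clinical detection, so they are bounds and not expectations. Counted from Day 1, the three-cycle gap vanishes. The net bias against the historical 15% is unknown, because the documents do not say how those patients were scanned; with similar scanning, part of the bias would be shared.

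**What to change.** State one time zero, reconciling Sections 4.6.4 and 10.4.1 and covering the pre-surgical infusions, and define month 6 in days. Keep the 8-weekly and End of Treatment scans. Moving the day-168 scan instead would leave six-cycle patients unscanned from day 112 to days 183-196, which is 71 to 84 days against the plan's own 8-week interval.

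Anchor the already planned two-monthly follow-up MRI to time zero so that one falls at month 6 for every progression-free patient on any path. Use a short window that does not open before month 6, for example weeks 26-28, aiming for the first week. Count a progression found at that scan as a PFS6 failure.

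Use the same class in the Simon count and in Kaplan-Meier, with one missing-scan rule. For example, class the patient as progression-free at month 6 if a later scan shows no progression, and otherwise as a failure at month 6. Add a sensitivity analysis that reverses this class in both.

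The cost is a calendar amendment and a short classing rule. Six-cycle patients have two MRIs about two weeks apart (day 168-169 and about day 183) and, depending on the anchor otherwise used, possibly one more follow-up MRI in the first year. Late scans slightly lower apparent PFS6. Spread evenly over days 183-189, false-go is 0.071 and power 0.675; over days 183-196, 0.060 and 0.65. If the historical 15% came from sparser scanning, the comparison also becomes somewhat stricter.
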